#### DEFINITION AND MANAGEMENT OF ON-TREATMENT ALT FLARES

On treatment flares will be managed per guidelines defined in Table 4. Post treatment ALT flares are defined as ALT  $\geq$  grade 2 CTCAE score, and participants will be followed every 4 weeks till ALT falls below grade 2 CTCAE score. Severe post-treatment flares are defined as ALT  $\geq$  grade 3 CTCAE score. Participants with post treatment severe ALT flares will be evaluated every week with until ALT decreases below CTCAE grade 3, then will be seen every 4 weeks for ALT between CTCAE grades 2-3, after which scheduled visits will resume per study protocol.

Subjects who experience post-treatment flares may undergo an evaluation for other causes of liver disease, as well as may be initiated on Peg-interferon alpha per discretion of the study investigator.

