#### **Secondary End Points:**

1. Sustained undetectable HDV RNA in serum at weeks 12 and 24 post treatment follow up.
2. Reduction in histologic inflammatory scores (modified HAI) by at least two points with no progression in histologic fibrosis (Ishak) at week 24 post-treatment follow-up.
3. Normalization of serum ALT (ALT <20 in females and ALT <31 in males) at the end of therapy, at week 12 of post-therapy follow-up and at week 24 of post-therapy follow-up, OR reduction in serum ALT by >50% of baseline at week 12 of post therapy follow up and week 24 of post therapy follow up.
4. Reduction in hepatic venous pressure gradient (HVPG) measurements by >25% of baseline OR normalization of HVPG (<5 mm Hg) at end of therapy.
5. Reduction in Fibroscan® transient elastography values by >25% of baseline at end of therapy.

6. Loss of HBsAg from the serum at the end of therapy, at week 12 of post-therapy follow-up or at week 24 of post-therapy follow-up.
7. Changes in quantitative HBsAg levels at the end of therapy and at week 24 of post therapy follow up, compared to baseline.
8. Changes in symptom scale measurements and quality of life before, during and after therapy.
9. Changes in the fecal microbiome before and after treatment.

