17. EKG

**Post Treatment Monitoring**

Patients will return for outpatient visits per the following schedule. As interferon alpha is the only recommended therapy for HDV, if a patient has been previously treated with interferon, there is no additional therapy to be offered. It is not planned to routinely offer interferon alpha to all patients after participating in this study. However, if a prolonged HDV flare with significant liver damage is demonstrated, rescue therapy with interferon alpha will be offered. Patients failing experimental therapy will not be excluded from therapy with standard interferon alpha.

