#### **Monitoring of Patients Discontinuing Therapy**

Therapy will be stopped for intolerance to lonafarnib, ritonavir and/or lambda (which is carefully defined in table 4). Patients who stop therapy due to intolerance, withdraw because of an adverse event, self-discontinue therapy or drop out from the study will be considered as treatment failures. Patients in whom therapy is stopped early or who discontinue treatment on their own will initially be followed in the same manner as those who do not respond as defined in the protocol. After treatment is discontinued, the patient will be followed for at least 24 weeks with visits to the outpatient clinic as per the post-treatment monitoring schedule described above. Thereafter, patients may be followed on an unscheduled basis under protocol 91-DK-0214 as is typical for patients who have participated in studies done by the Liver Diseases Branch.

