An additional risk that may be encountered with the therapy of HDV includes an increase in liver function tests during and after therapy, the risk of a flare in HBV ( $\geq 2$  log increase and a total HBV DNA over 2,000 IU/mL) as the HDV viral load goes down, and an increase in HDV viral load after therapy is ended. Flares in liver function tests are not uncommon with the start of treatment of HBV disease and necessitate a careful and frequent review of liver function tests. We will treat all the patients with nucleoside analogues for HBV, the selection being made by the investigator based on the subject's condition and history of prior anti-HBV therapy. It should also be noted, that lonafarnib has undergone extensive analysis and has exhibited neither synergy nor antagonism in combination with the 5 available HBV antiviral medications. A flare in HDV viral load after termination of lonafarnib will be monitored closely and interferon therapy may be started as determined by the investigator. It should be noted that when interferon is used for HDV it is typically given for a year, and cessation of therapy may be associated with flares of HDV.

11. ***The risks and hazards of Ritonavir therapy.*** Ritonavir is an orally bio-available protease inhibitor, which was used as a pharmacokinetic booster (coadministration of 100mg Ritonavir) of second protease inhibitor or other anti-retroviral agents. In this study, ritonavir will be used as a pharmacokinetic booster of Lonafarnib. The most common side effects (>10%) of ritonavir are nausea, diarrhea, vomiting, altered sense of taste (taste perversion), abdominal pain, arthralgia, back pain, cough and loss of appetite. If it is used more than 60 days, there is increase in cholesterol levels and triglycerides, as well as blood sugar, potentially resulting in the development of diabetes mellitus. The increase in cholesterol and triglycerides can occur within one week of taking this medication. Lipid profile should be monitored prior to initiating therapy and at periodic intervals during therapy. After the completion of the study, cholesterol and triglyceride levels should return to baseline.
  - a. Elevation of AST/ALT can exceed 5 times the upper limit of normal, clinical hepatitis and jaundice in patients receiving Ritonavir alone or in combination with other antiretroviral drugs. Dosage adjustment is not necessary in patients who have mild (Child- Pugh Class A) to moderate

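### The failure rule omits patients who complete treatment and then receive interferon alpha, so a post-rescue biopsy could be credited to the triple regimen (secondary endpoints only, probably small)

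*Combined protocol and SAP*

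**What the plan says.** All references are to the combined protocol and SAP. Three sections allow interferon alpha after study treatment ends:

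- Definition and Management of On-Treatment ALT Flares: a patient with a post-treatment flare (ALT grade 2 or higher) "may be initiated on Peg-interferon alpha per discretion of the study investigator". Flared patients then return to the scheduled visits.
- Post Treatment Monitoring: "if a prolonged HDV flare with significant liver damage is demonstrated, rescue therapy with interferon alpha will be offered". Routine interferon is not planned.
- Hazards and Discomforts, lonafarnib risks: after an HDV viral-load flare, "interferon therapy may be started as determined by the investigator". No numeric threshold is given.

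The scoring rule is under Monitoring of Patients Discontinuing Therapy. Patients who stop for intolerance, withdraw because of an adverse event, "self-discontinue therapy or drop out from the study will be considered as treatment failures".

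Secondary End Points asks for an inflammatory-score fall of at least two points "with no progression in histologic fibrosis (Ishak) at week 24 post-treatment follow-up". ALT normalization is judged "at the end of therapy, at week 12 of post-therapy follow-up and at week 24 of post-therapy follow-up". HBsAg loss may be shown at the end of therapy, "at week 12 of post-therapy follow-up or at week 24 of post-therapy follow-up". None of these carries a condition about rescue, and Design of the Trial/Statistical considerations has no rule for it.

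**The concern.** The follow-up endpoints are meant to show what the regimen leaves behind once it stops, and the Precis describes this period as off therapy. A patient who completes 24 weeks, flares, starts interferon alpha and stays in follow-up meets none of the listed failure conditions. If that patient's week-24 biopsy then improves on baseline, the rules as stated score a histologic response to the triple regimen. The trial is open-label with a single arm, so no control group would reveal the effect. The investigator decides on rescue, which is a reason to fix the scoring before results are known.

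**Working it through.** **Figures in the plan.** No planned figure is in dispute. Inputs: 26 patients and 30% dropout (Design of the Trial/Statistical considerations), so 26 × 0.70 = 18.2, or about 18 completers. The number of rescues is not given and is treated as an assumption.

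**Step 1: does any rule catch the rescued completer?** The failure list does not, because the patient neither stopped early nor dropped out. The endpoint definitions and the statistical section do not either. Post Treatment Monitoring mentions patients failing experimental therapy, but only to preserve their access to interferon; it does not say how they are scored.

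**Step 2: how likely is rescue?** The ALT-flare trigger is grade 2. On the modified scale in Table 5, grade 2 starts above 5 times the patient's own baseline, if that scale governs the flare section. Post Treatment Monitoring needs a prolonged flare with significant liver damage. Only the viral-load route has no threshold. Hazards and Discomforts reports 5 post-treatment ALT flares in LOWR-4, an earlier lonafarnib study, all with normal liver function. Rescue should be uncommon and may not occur.

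**Step 3: how much interferon before each reading?** Physician visits with routine labs fall at post-treatment weeks 1, 2, 4, 8, 12, 16 and 20.

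| Start week | Weeks before week-24 reading | Weeks before week-12 reading |
|---|---|---|
| 1 | 23 | 11 |
| 2 | 22 | 10 |
| 4 | 20 | 8 |
| 8 | 16 | 4 |
| 12 | 12 | 0 |
| 16 | 8 | – |
| 20 | 4 | – |

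The maxima are therefore about 23 and 11 weeks.

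**Step 4: exposure by endpoint.**

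- *Histology, most exposed.* Secondary End Points, the schedule text and Table 1 put the repeat biopsy at post-treatment week 24, and no earlier reading has to be met. (The Precis alone puts it at the end of treatment.)
- *Quantitative HBsAg, less exposed.* It also has an end-of-therapy reading. Post-therapy symptom and microbiome changes are similarly open.
- *HBsAg loss, exposed in form but unlikely.* Any one time point suffices. Background reports 23% seroconversion at the end of a peginterferon study lasting up to 5 years. At a constant rate, 23 weeks gives 1 − 0.77^(23/260) = 2.3%; if the 23% was reached by 3 years, 1 − 0.77^(23/156) = 3.8%.
- *Sustained HDV RNA and ALT, partly protected* if every listed visit must be met. An early rescue then has at most about 11 weeks to work by week 12, and a relapse after a good week-12 reading leaves under 12 weeks to week 24. For HDV RNA, the lambda section of Background gives 15/91 = 16.5% negative by week 8 of peginterferon alpha and 19/91 = 20.9% by week 12. If those rates applied, an early rescue adds 0.165/26 = 0.6 to 0.209/26 = 0.8 points. If the ALT visits are read separately, which the wording leaves open, week-24 ALT is exposed on its own.
- *HVPG, conditional.* The endpoint is "normalization of HVPG (<5 mm Hg) at end of therapy", which is before rescue. It is exposed only if the measurement is taken with the post-treatment week-24 biopsy, as Study Procedures and Schedule and Table 1 have it.
- *Unaffected:* both primary endpoints and end-of-therapy Fibroscan, all complete before follow-up.

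**Step 5: size for histology.** If k rescues each yield a response, the rate rises by k/N.

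| Rescues | N = 26, every rescue responds | 18 completers, every rescue responds | N = 26, 39% respond |
|---|---|---|---|
| 0 | 0 | 0 | 0 |
| 1 | 3.8 points | 5.6 points | 0.39/26 = 1.5 points |
| 2 | 7.7 points | 11.1 points | 3.0 points |

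The 39% comes from Background: histologic improvement or loss of serum HDV and HBsAg at 3 years of peginterferon. It is generous here, being a composite reached over a far longer course. For scale, the exact 95% interval around 13/26 runs from 29.9% to 70.1%.

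**The case against.** The strongest case against is that this is too small to matter. A rescued patient has just flared, needs a two-point inflammatory fall from the pre-treatment baseline without fibrosis progression, and has had at most about 23 weeks of a drug that Hazards and Discomforts says is typically given for a year. No secondary endpoint carries a test or decision threshold. Concomitant medications are recorded, so rescued patients could be identified later. Reporting outcomes regardless of rescue, with rescues disclosed, is also a defensible choice. The protocol's own phrase about patients failing experimental therapy suggests nobody means to credit them.

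Most of this stands as a limit on size. It does not supply the missing rule. The plan already scores other post-baseline events as failure and describes follow-up as off therapy, so extending the rule to rescue fits its own logic. The plan has not stated the alternative of counting outcomes regardless of rescue either.

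A reader might infer that every rescue inflates the histologic rate by 3.8 points. That holds only if every rescue succeeds, which nothing in the documents supports. A reader might also infer that HBsAg loss and sustained HDV RNA are materially inflated; the rates in Background and the two-visit requirement argue against it.

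**Conclusion.** The gap is real and minor. As written, a completer rescued with interferon alpha can count as a histologic responder at post-treatment week 24, with lesser exposure for quantitative HBsAg and for HBsAg or ALT judged at a single visit. The contribution per rescue is at most 3.8 points at 26 patients (5.6 at 18 completers), and about 1.5 points on the borrowed 39% rate. The number of rescues is unknown, expected to be low, and possibly zero.

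The conclusion rests on a literal reading of the failure list and on the biopsy being taken at post-treatment week 24. The view that rescue is uncommon also assumes that the modified ALT scale applies to post-treatment flares. Direction is not certain for every endpoint, since the flare may itself worsen histology. The documents do not support a claim that the trial's primary efficacy or tolerability result is affected.

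**What to change.** Add to Monitoring of Patients Discontinuing Therapy, with a cross-reference in Secondary End Points: a patient who starts interferon alpha or other anti-HDV therapy after study treatment is a non-responder for every responder endpoint assessed after that start date; HBsAg loss documented before rescue still counts. Apply the same rule to HVPG if it is read at post-treatment week 24. For change endpoints (quantitative HBsAg, symptom scale, microbiome), report post-rescue values separately. State the number rescued and the start week.

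The cost is a sentence or two of text. Concomitant medications are already reviewed at physician visits through study week 48 (Study Procedures; Table 1), so no new data, visits or patients are needed. The downside is that secondary durability rates may be slightly less favourable. If nobody is rescued, nothing changes.

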**Table 6: Post treatment ALT flare management schedule**

ALT (CTCAE grade)	Intervention/Management	Follow up schedule
$\geq 2-3$	Labs per protocol 1. Liver panel 2. CBC 3. PT/INR	Every 4 weeks, till ALT < Grade 2 CTCAE, then resume visits per study protocol.
$\geq 3$	Labs per protocol 1. Liver panel 2. CBC 3. PT/INR	Every week, till ALT < Grade 3 CTCAE, then every 4 weeks till ALT < Grade 2 CTCAE, then resume visits per study protocol.

## **DATA AND SAFETY MONITORING**

The Principal Investigator will function as the data and safety monitor and report any adverse events to the IRB. The Principal and Associate Investigators in this protocol will monitor data and safety. The Liver Diseases Branch, NIDDK, reviews data and safety weekly in clinical research rounds. These rounds are separate from regular clinical rounds and consist of review of all study patients including flow sheets of major safety and efficacy measurements. Additionally, an outside data/safety monitor will be utilized. [name], MD from the Division of Gastroenterology and Hepatology at the University of Maryland Medical Center, Baltimore, MD will serve as the data/safety monitor and will review data every two weeks during the course of the study, or sooner based on clinical necessity. Yearly reports are made to the NIDDK/NIAMS IRB regarding safety and efficacy.

## **DATA MANAGEMENT PLAN**

Data will be maintained electronically on electronic case report forms (eCRF). Data reported in the eCRF derived from source documents should be consistent with the source documents or the discrepancies should be explained and captured in a progress note and maintained in the participant's official electronic study record. Clinical data (including AEs, concomitant medications, and expected adverse reactions data) and clinical laboratory data will be entered into CRIS, which is 21CFR Part 11 compliant, and into REDCap, both of which are maintained at the NIH Clinical Center. The data systems include password protection and internal quality checks, such as automatic range checks, to identify data that appear inconsistent, incomplete, or inaccurate. Clinical data will be entered directly from the source documents. Information derived from patient interview will be entered to eCRFs and considered source documents.

## **REPORTING OF ADVERSE EVENTS, UNANTICIPATED PROBLEMS AND DEVIATIONS**

Reportable events will be tracked and submitted to the IRB as outlined in Policy 801.

## **FDA AND SPONSOR REPORTING REQUIREMENTS**

The study investigator will immediately report to the sponsor any serious adverse event, whether or not considered study intervention related, including those listed in the protocol or investigator brochure and must include an assessment of whether there is a reasonable possibility that the study intervention caused the event. Study endpoints that are serious adverse events (e.g., all-cause mortality) must be reported in accordance with the protocol unless there is evidence suggesting a causal relationship between the study intervention and the event (e.g., death from anaphylaxis). In that case, the investigator must immediately report the event to the sponsor.

All serious adverse events (SAEs) will be followed until satisfactory resolution or until the site investigator deems the event to be chronic or the participant is stable.

The study sponsor will be responsible for notifying the Food and Drug Administration (FDA) of any unexpected fatal or life-threatening suspected adverse reaction as soon as possible, but in no case later than 7 calendar days after the sponsor's initial receipt of the

information. In addition, the sponsor must notify FDA and all participating investigators in an Investigational New Drug (IND) safety report of potential serious risks, from clinical trials or any other source, as soon as possible, but in no case later than 15 calendar days after the sponsor determines that the information qualifies for reporting.

### **REGULATORY REQUIREMENTS**

The IND associated with this study (113137), in which the NIDDK is the sponsor, is associated with lonafarnib and lambda interferon. The FDA has not requested an IND for the use of ritonavir in combination with lonafarnib. Study procedures will be subject to audits and/or monitoring visits to ensure compliance with the protocol and applicable regulatory requirements consistent with the NIDDK quality assurance program plan and applicable FDA guidelines. Audit and/or monitoring visit results will be reported to the Principal Investigator for further reporting as appropriate. Study documents and pertinent hospital or clinical records will be reviewed to verify that the conduct of the study is consistent with the protocol plan.

### **RECRUITMENT STRATEGY**

We will advertise on the NIH web site and through letters sent to local physicians and clinics for patients.

#### **Recruitment of Women, Minority Individuals and Children.**

Delta hepatitis is a rare disease in the general population. The major risk factors are injection drug use and hemophilia. It is rare to find the disease in childhood, the majority of children with delta hepatitis being immigrants from areas of the world where it is common (Eastern Europe, Amazon Basin). In addition, hepatitis is often mild in children. Finally, FTIs have not been adequately evaluated for safety and efficacy in children. We therefore do not plan to recruit children below the age of 18.

Women are less likely to have HDV, as one of the risk factors, hemophilia is a disease of males. Notwithstanding this, every effort will be made to find both women and members of minorities with HDV. To increase the representation of both women and minority individuals in this trial, we plan to advertise widely.

### **CONSENT PROCESS**

Informed consent begins with the initial approach of an investigator to a potential subject (for example through a flyer or advertisement) and continues (a) until the completion of the research study, (b) until the individual completes study participation, (c) the subject withdraws him/herself from the study or (d) the subject is withdrawn from the study by the investigator.

Written informed consent will be obtained from the participant prior to any screening visits, study procedures or treatments. The Principal Investigator or other designated qualified protocol investigators will explain the study in language understandable to the subject. Sufficient time and opportunity will be given for discussion of the research as well as to answer any questions they may have, taking care to minimize or eliminate the perception of coercion or undue influence. The participant and the investigator will sign

the current IRB-approved informed consent document. A copy of the consent will be given to the subject for future reference. The signed documents will be sent to the Medical Records Department for placement in the subject's permanent CC medical record. The consent process will additionally be documented in the electronic medical record (CRIS).

#### **RESEARCH USE, STORAGE AND DISPOSITION OF HUMAN SUBJECT'S SAMPLES AND DATA.**

Patients will have serum and stool stored from selected time points during this study. The serum specimens will be used for repeat virological testing and special tests as needed and the stool tests will be used for microbiome analysis. Samples may be used to assess factors associated with response or non-response to therapy. These samples will be tested in the Liver Diseases Branch or the routine clinical services of the Clinical Center. Residual samples may be used for future research related to liver disease and its' associated conditions. If residual samples are evaluated by outside collaborators in the future, this will be done so only after all identifying data have been removed from all samples and all applicable tech transfer are initiated. ARUP and The Doctors Laboratory will perform all HDV RNA quantitative testing for this protocol. All samples sent to outside collaborators, ARUP and The Doctors Laboratory will be numbered and a key to the number system will be stored and backed up by the principal investigator of this study. Research records and data as well as sera will be stored indefinitely in our locked offices and freezers, the medical record department and the pathology department. These materials will be protected and tracked by standard operating procedures in the medical record as well as a compulsive filing system in our locked offices and freezers. There will be redundant storage of clinical information in the medical record department and our offices. Computer files will be maintained on password-protected computers and servers. Serum samples will be processed and stored by the NIDDK core laboratory facility. These samples will be stored in locked freezers inside locked rooms. Access to these samples will require written approval from the Liver Diseases Branch chief, and will be recorded by the LDB and by the core laboratory. This should minimize the risk of loss or destruction of information and specimens. If that were to occur we would report it to the IRB. We do not plan to destroy this personal medical information or research subject sera after completion of the study because it may be critically important for physicians (here or elsewhere) to have access to this information when caring for these patients in the future. If requested, Eiger Biopharmaceuticals (who will be providing the Lonafarnib, Ritonavir and Lambda), will have access to the clinical data only after all personal identifiers have been removed. They will also be included in all serious adverse event notifications.
